2.3 Exploratory objectives

- To assess the effect of esomeprazole 40 mg, omeprazole 80 mg or lansoprazole 60 mg on the PD profile of clopidogrel by assessing change in platelet reactivity index (ΔPRI), derived from flowcytometric assay (VASP) results, at Days 2, 6, 15, and 30 relative to baseline.
- To assess the effect of esomeprazole 40 mg, omeprazole 80 mg or lansoprazole 60 mg on the pharmacodynamic (PD) profile of clopidogrel excluding low responders (mIPA of 25% or less at Day 2 when receiving clopidogrel alone) by assessing maximum inhibition of platelet aggregation (mIPA) at Days 2, 6, 15, and 30 relative to baseline.

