6.6 CYP2C19 Genotyping

6.6.1 Collection of pharmacogenetic samples

A mandatory blood sample for *CYP2C19* genotyping will be obtained on Day -1. No other research will be performed on the samples. Samples will be collected, handled, labelled, stored and shipped as detailed in the Laboratory Manual.

For blood volume see Section 7.1.

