12.2.5 Pharmacodynamics

Descriptive statistics will be used to summarize mPA, and mIPA, in volunteers by treatment and by day. In addition, VASP data (PRI and Δ PRI) will be summarized using descriptive statistics by treatment and by day. All PD variables will be presented in listings.

Pharmacodynamic comparison of test treatments (esomeprazole + clopidogrel, omeprazole + clopidogrel, or lansoprazole + clopidogrel) to the reference treatment (clopidogrel alone) will be assessed for each of the PD endpoints – mIPA and Δ PRI. These PD endpoints for each of the test treatments will be compared with the corresponding PD endpoints for the reference

treatment. Comparisons between the test and reference treatments will be made by using a mixed effects analysis of variance (ANOVA) model with fixed-effects for treatment, period, site, and sequence. Volunteers within sequence will be included as a random effect in the model. Log-transformations may be used to meet model assumptions. The linear contrasts subtracting the least-squares means for the reference treatment from the least-squares means for the test treatment will be estimated to obtain least square estimates of the difference in least square means and the corresponding 90% CI. P-values will also be presented.

The above analysis will be repeated on mIPA excluding volunteers defined as clopidogrel low responders (mIPA response of 25% or less at Day 2) when receiving clopidogrel alone.

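### The exploratory low-responder analysis selects volunteers on the same Day 2 reference value it then compares against, which biases the Day 2 contrast towards a PPI-induced loss of inhibition

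*Protocol*

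**What the plan says.** The protocol synopsis and Section 2.3 set an exploratory objective: to assess the effect of each PPI on mIPA "excluding low responders (mIPA of 25% or less at Day 2 when receiving clopidogrel alone"). Section 2.3 says this is done "by assessing maximum inhibition of platelet aggregation (mIPA) at Days 2, 6, 15, and 30 relative to baseline", so Day 2 is one of the analysed days.

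Section 12.2.5 gives the analysis: "The above analysis will be repeated on mIPA excluding volunteers defined as clopidogrel low responders (mIPA response of 25% or less at Day 2"), where the Day 2 value is the one on clopidogrel alone. The main comparison that is repeated is a mixed model with clopidogrel alone as reference: "The linear contrasts subtracting the least-squares means for the reference treatment from the least-squares means for the test treatment" are estimated, with 90% confidence intervals and p-values.

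The protocol has no run-in or other separate measurement from which to classify responders. It does collect a mandatory blood sample for CYP2C19 genotype (Section 6.6.1: "genotyping will be obtained on Day -1. No other research will be performed on the samples"), and Section 10 has the genotype merged with the clinical data before the statistical analysis.

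**The concern.** Day 2 mIPA on clopidogrel alone has two jobs in this analysis. It decides who is kept, and for those who are kept it is the reference outcome. The selection therefore acts on one side of the comparison only. A volunteer with an unluckily low reference value is removed. A volunteer with an equally unlucky value in a PPI period is not.

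Among those retained, the reference errors are positive on average and the PPI errors are centred on zero. A random effect for volunteer does not correct this, because the selection acts on the period-specific error and not only on the volunteer's own level.

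At stake is the reading of an exploratory result reported with intervals and p-values. On Day 2 it is pushed in the same direction for all three PPIs, towards a loss of platelet inhibition.

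**Working it through.** **The plan's own precision figure.** Section 12.3 uses n = 54 and an SD of the paired difference of 14, and claims a 95% CI of length at most 9 with at least 96% probability.
- The length is 2·t(0.975, 53)·s/√54. The chi-square distribution of s² gives P(length ≤ 9) = 0.967, so the claim reproduces.
- 54/(2/3) = 81, also as stated.

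**Inputs for the bias.**
- Within-volunteer SD: sw = 14/√2 = 9.9, so sw² = 98 (from Section 12.3, with equal independent errors in each period).
- Cut-off: 25 (Sections 2.3 and 12.2.5).
- Mean Day 2 mIPA on clopidogrel alone, μ, and between-volunteer SD, sb: not in the protocol. Assumed ranges are 30 to 60 and 10 to 20.
- True PPI effect: zero.

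**Formula.** Let sT = √(sw² + sb²), a = (25 − μ)/sT and λ = φ(a)/(1 − Φ(a)). Among volunteers whose reference value exceeds 25:
- mean reference value = μ + sT·λ
- mean PPI value = μ + (sb²/sT)·λ
- expected test minus reference = −(sw²/sT)·λ

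**Worked case, μ = 40 and sb = 15.** sT = √(98 + 225) = 17.97; a = −15/17.97 = −0.835; λ = 0.353. The retained reference mean is 40 + 17.97 × 0.353 = 46.3 and the retained PPI mean is 40 + 12.52 × 0.353 = 44.4. The difference is −1.92, with 20.2% of volunteers excluded.

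**Day 2 bias with no true effect (percentage units; share excluded in brackets).**

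| Mean Day 2 mIPA | sb = 10 | sb = 15 | sb = 20 |
|---|---|---|---|
| 30 | −4.1 (36%) | −3.4 (39%) | −2.9 (41%) |
| 40 | −1.8 (14%) | −1.9 (20%) | −1.9 (25%) |
| 50 | −0.6 (4%) | −0.9 (8%) | −1.1 (13%) |
| 60 | −0.1 (0.6%) | −0.3 (3%) | −0.5 (6%) |

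Over this table the standard error of one contrast is about 1.9 to 2.5.

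**Simulation check.** The simulated trials had 81 volunteers, each on the reference and two of the three PPIs. Paired t-tests on the retained pairs stood in for the full mixed model, with two-sided 5% tests. The simulated biases match the formula.
- Rejection rates with no true effect were 21–42% at mean 30, 12–16% at mean 40 and 6–8% at mean 50.
- With no exclusion, the bias was about zero and rejection 4–6%.

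**Later days.** With uncorrelated errors within a period, the bias on a later day was about zero. At a correlation of 0.5 it was about half the Day 2 value (with sb = 10, −2.1 at mean 30 and −0.9 at mean 40). Some correlation is plausible, because Section 11.3 divides every day's value in a period by the same baseline.

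**Reading of the 14.** Section 12.3 derives it from a root MSE. If 14 were the within-volunteer SD itself, the bias would be larger: 1.7 to 2.2 units at mean 50 and 5.4 to 7.1 at mean 30, in the same direction.

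**The case against.** The strongest reply is that little hangs on this. The analysis is exploratory, it repeats the main one, and no decision rule is attached to it. The primary comparison and the sample size rest on all volunteers. This stands and limits the weight of the point.

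The size also cannot be fixed from the protocol. If mean Day 2 mIPA is 50 or more, the bias is about 1 unit or less and the rejection rate is close to nominal. The largest figure, −4.1, needs a mean of 30, with 36% of volunteers called low responders. This stands too. The direction of the bias is certain under the stated rule, but its importance is not.

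The research hypothesis in Section 1.2 is that the PPIs differ from one another. The same upward shift of the reference enters all three contrasts, so it largely cancels when one PPI is set against another. That is right, but the contrasts Section 12.2.5 specifies are each PPI against clopidogrel alone, and there it does not cancel.

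A genotype rule also changes the question somewhat. Section 1.3 names several enzymes in clopidogrel activation, so the genotype group is not the phenotypic low-responder group. This is a real cost.

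A reader might add that volunteers who withdraw before their clopidogrel-alone period cannot be classified. How to handle them is ordinary detail for the SAP and is not counted here as a defect of the protocol.

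**Conclusion.** The point holds for the exploratory low-responder analysis on Day 2. The stated rule produces a one-directional error: about −2.9 to −4.1 units at a mean Day 2 mIPA of 30, −1.9 at 40, −0.6 to −1.1 at 50 and −0.1 to −0.5 at 60. For scale, the trial is sized for a 95% CI no longer than 9 units, a half-width of 4.5. The figures rest on a normal model, equal and independent period errors with SD 9.9, and assumed values for the mean and the between-volunteer SD.

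A reader might infer that the trial will report a PPI interaction that does not exist, or that its main result is compromised. The documents support neither. The primary analysis keeps all volunteers and is unaffected. The bias may be small if few volunteers fall at or below 25%. Days 6, 15 and 30 are biased only as far as errors within a period are correlated, and the protocol gives no such correlation.

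**What to change.** In the synopsis, Section 2.3 and Section 12.2.5 together, define the excluded subgroup by CYP2C19 genotype group from the mandatory Day -1 sample, with the grouping fixed before PD data are seen. Genotype does not depend on the error in any period, so it does not cause this regression to the mean.

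If the 25% rule is kept as well, report it as a descriptive sensitivity analysis. State that its Day 2 contrast is biased by selection, and give no p-value and draw no interaction conclusion from it.

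Defining low responders by mean Day 2 mIPA over all of a volunteer's periods is not a general cure. With no PPI effect its bias is about zero, but it selects on the PPI response when that varies between volunteers. With an assumed true mean effect of −10, effect SD 8 shared across PPIs, mean mIPA 40 and between-volunteer SD 15, it gave −8.7 with 31% excluded. It should not be presented as unbiased.

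The cost is a small protocol edit in three places, which is more than SAP wording because an objective changes, and a subgroup that does not coincide with the phenotypic low responders. No new data are needed.

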12.3 Determination of sample size

The study is sized to estimate the absolute mean difference in mIPA with and without the PPI with a specified precision. With 54 volunteers, a 95% CI with length of at most 9 percentage units is achieved with at least 96% probability. As each of the 3 PPIs is included in two-thirds of the planned treatment sequences, a total of 81 volunteers are required. Assuming a 20% dropout rate for this study, 101 volunteers will be enrolled to ensure 81 volunteers complete the study.

The calculation assumes an SD of paired difference of 14% units, derived from the root MSE of the analysis of internal data on ADP-induced maximum extent IPA for %mIPA (20 μ M ADP).

13.2 Overdose

Clopidogrel- refer to the "Overdose" section of the official prescribing information at http://products.sanofi-aventis.us/PLAVIX/PLAVIX.html

Esomeprazole-refer to the "Overdose" section of the official prescribing information at http://www1.astrazeneca-us.com/pi/Nexium.pdf

Omeprazole- refer to the "Overdose" section of the official prescribing information at http://www1.astrazeneca-us.com/pi/Prilosec.pdf

Lansoprazole- refer to the "Overdose" section of the official prescribing information for PREVACID® at http://www.tpna.com/products/default.aspx

If an overdose on an AstraZeneca study drug occurs in the course of the study, then investigators or other site personnel inform appropriate AstraZeneca representatives within 1 day, ie, immediately but no later than the end of the next business day of when he or she becomes aware of it.

The designated AstraZeneca representative works with the Investigator to ensure that all relevant information is provided to the AstraZeneca Patient Safety data entry site.

For overdoses associated with SAE, standard reporting timelines apply, see Section 6.3.4. For other overdoses, reporting should be done within 30 days.

13.3 Pregnancy

All outcomes of pregnancy should be reported to AstraZeneca.

Females of childbearing potential must adhere to the birth control methods outlined in Section 4.1. Male volunteers must refrain from fathering a child, including sperm donation, during the study and 3 months following the last dose. If the investigator receives information that a pregnancy has occurred during the study (including pregnancy in the partner of a male volunteer) despite these restrictions, the designated Quintiles representative should be informed

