4.1 Inclusion criteria

For inclusion in the study volunteers must fulfill the following criteria:

- 1. Provision of written informed consent prior to any study specific procedures.
- 2. Healthy males within age of 18-45 years and females within age of 18-55 years with suitable veins for cannulation or repeated vein puncture. Females volunteers must

be of nonchildbearing potential (post-menopausal, had a hysterectomy and/or bilateral oophorectomy) or be of childbearing potential and have a negative serum hCG pregnancy test on Day -1. Female subjects of childbearing potential must consent to using 1 clinically accepted method of contraception for 10 days before receiving the first dose of study medication, throughout the entire study including each washout, and for 1 month after completion of the study. Clinically accepted methods of contraception that may be used by the subject and/or partner include: diaphragm with spermicide, IUD (except for Mirena®), condom with spermicidal foam, or condom with vaginal spermicide.

- 3. Weight of 50-95 kg, inclusive, and a BMI between 19-30 kg/m², inclusive.
- 4. No clinically significant abnormal findings as judged by the Investigator on enrollment physical exam.

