- 5. Volunteers should refrain from strenuous physical activity, which is not within the volunteer's normal daily routine, and any activities that have a risk of trauma from 7 days prior to admission to the unit until after the final medical examination at the study follow-up.
- 6. Abstain from blood and plasma donation during the study and until three months after the final medical examination at the study follow-up.

- 7. Female volunteers of childbearing potential must consent to using 1 clinically accepted method of contraception for 10 days before receiving the first dose of study medicaiton, throughout the entire study including each washout, and for 1 month after completion of the study. Clinically accepted methods of contraception that may be used by the subject and/or partner include: diaphragm with spermicide, IUD (except for Mirena®), condom with spermicidal foam, or condom with vaginal spermicide.
- 8. Not participate in any other clinical study.
- 9. Volunteers will be served standardized meals during the inpatient visits. Excessive intake of caffeine (greater than 5 cups of coffee or equivalent) should be avoided during the washout periods and prior to final follow-up.
- 10. Male volunteers and their partners should use appropriate contraception (double barrier method or vasectomy) throughout the entire study starting from the 1st dose of study medication including each washout and refrain from sperm donation until at least 3 months after the last dose of study medication, since no data on male reproduction is available.

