6.2.1 Follow up procedures

A follow up visit will be scheduled at least 7 days after the last dose of study drug. This visit will include a check for concomitant medications and AEs, collection of blood and urine samples for clinical chemistry, (hCG- females only), hematology and urinalysis, assessment of vital signs, weight, pECG, and a physical examination.

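### Male contraception (Section 5.1) and the ban on fathering a child (Section 13.3) run for different periods, and Section 13.3 leaves unclear which pregnancies must be notified

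*Protocol*

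**What the plan says.** **Men, restriction list.** Protocol Section 5.1 item 10 reads: "Male volunteers and their partners should use appropriate contraception (double barrier method or vasectomy) throughout the entire study", counted from the first dose and including the washouts. The same sentence goes on to say that men should "refrain from sperm donation until at least 3 months after the last dose of study medication". The reason given is the absence of data on male reproduction.

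**Men, pregnancy section.** Section 13.3 reads: "Male volunteers must refrain from fathering a child, including sperm donation, during the study and 3 months following the last dose".

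**Women.** Section 4.1 item 2 and Section 5.1 item 7 both require contraception from 10 days before the first dose, "throughout the entire study including each washout, and for 1 month after completion of the study". Section 13.3 adds no separate female period and refers back: "Females of childbearing potential must adhere to the birth control methods outlined in Section 4.1".

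**Notification.** Section 13.3 opens with a sentence, without a time limit, that pregnancy outcomes are to be reported to the sponsor. After the two restrictions comes the operative trigger: "If the investigator receives information that a pregnancy has occurred during the study". It includes partners of male volunteers, is tied to the restrictions just listed, and directs the notice to the contract research organization's representative.

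**Where the study ends.** Section 6.2.1: "A follow up visit will be scheduled at least 7 days after the last dose of study drug". Section 6.3.3 stops recording of serious adverse events at that visit. Section 9.5 defines the end of the study at trial level, as the last volunteer's last visit.

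The amendment text at hand changes neither Section 5.1 item 10 nor Section 13.3.

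**The concern.** Two things do not line up.

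First, the two statements of the male rule differ in scope. Item 10 attaches the post-dose period to sperm donation and gives contraception no extension beyond the study. Section 13.3 applies the same 3 months to fathering a child in any way. Section 5.1 is the list volunteers are told to comply with; Section 13 is headed as procedures for the investigator. A site that briefs men from Section 5.1 alone would not convey the wider duty.

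Second, the notification trigger refers to pregnancies that occur despite the restrictions, yet limits itself to the study period, while those restrictions run on after it. A breach in the later part of either window falls outside the literal trigger. The untimed opening sentence may or may not bring it back in; a site cannot tell which sentence governs.

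At stake is volunteer and partner protection and the completeness of one safety outcome. The protocol itself treats male reproductive risk as an open question, so a late partner pregnancy is information it has reason to want.

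**Working it through.** **1. The protocol's calendar reproduces.**
- Treatment and washout: 3 × 30 + 2 × 14 = 118 days, as stated with Figure 1.
- Total: 21 (screening) + 118 + 7 (follow-up) = 146 days, as stated in the synopsis.

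**2. From last dose to last visit.**
- The last dose is on Day 29 of Period 3: 2 × (30 + 14) + 29 = day 117 of the 118.
- On the 146-day schedule the visit falls at 118 + 7 = day 125, that is 125 − 117 = 8 days after the last dose.
- The minimum in Section 6.2.1 is 7 days.

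**3. Male window beyond the volunteer's own last visit.** The protocol does not define a month in days. Assume 3 months is 90 to 92 days. Affected days = window − interval from last dose to follow-up.

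| Follow-up after last dose | 90 days | 91 days | 92 days |
|---|---|---|---|
| 7 days | 83 | 84 | 85 |
| 8 days | 82 | 83 | 84 |
| 14 days (later visit, for illustration) | 76 | 77 | 78 |

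In these days Section 13.3 still bars fathering a child, item 10 no longer asks for contraception, and a pregnancy is outside the literal trigger.

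**4. The same under the trial-level end of study (Section 9.5).** If a man's last dose falls *d* days before the last volunteer's last visit, the affected days are max(0, window − *d*). For the last volunteer, *d* is 7 to 8 and the result is again 82 to 85 days. For anyone with *d* of 90 to 92 days or more, it is zero.

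**5. Female window.** The restriction runs 1 month past completion. With 1 month assumed to be 28 to 31 days, and the study ending at the same point in Sections 4.1 and 13.3, those 28 to 31 days lie outside the literal trigger.

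**6. The texts side by side.**

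| Duty | Section 5.1 or 4.1 | Section 13.3 |
|---|---|---|
| Men, sperm donation | at least 3 months after last dose | 3 months after last dose |
| Men, contraception or not fathering a child | contraception during the study only | not fathering a child: study plus 3 months after last dose |
| Women, contraception | 1 month after completion | refers to Section 4.1 |
| Notification trigger | – | pregnancy during the study |
| Reporting of outcomes | – | no period stated |

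The second row is a mismatch. The last two rows leave the reporting period unclear.

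**The case against.** The strongest reply is that nothing here strictly conflicts. The female rule is the same in Sections 4.1 and 5.1, and Section 13.3 refers to it. The sperm-donation period agrees between Sections 5.1 and 13.3. The remaining male rules can both be obeyed, and nothing ranks Section 5.1 above Section 13.3. All of this stands. A reader might infer that the windows contradict each other, or that conception in the later male window is left unprevented; the documents do not support that, because Section 13.3 expressly prohibits it. What they show is a difference in scope.

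It can also be said that item 10 is one loose sentence whose 3 months may be meant to cover contraception too. That is possible but weak: item 7 of the same list spells out the female extension, and item 10 has no counterpart for male contraception.

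On reporting, a reader might infer that Section 13.3 covers only pregnancies during the study. The untimed opening sentence, and the link from the trigger to the restrictions, speak against so firm a reading. The right description is unclear. That still needs correction, since the sentences of one short section suggest different periods.

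Nothing in the protocol requires notification to match a precautionary contraception period, and Table 1 schedules hCG tests in women on Day -1, Day 15, Day 30 and at follow-up. Both points are fair, and differing periods for men and women are not an error. The female part of the point is therefore limited to the literal trigger being shorter than the restriction it cites.

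Finally, the consent form is not at hand, so what volunteers are actually told is unknown.

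**Conclusion.** The point holds as a wording mismatch in two places: male contraception in Section 5.1 item 10 against the fathering ban in Section 13.3, and an unclear reporting period within Section 13.3.

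The size of 82 to 85 days of the male window rests on three assumptions: the study means each volunteer's own participation, follow-up takes place 7 to 8 days after the last dose, and 3 months is 90 to 92 days. A later visit shortens the gap, and the trial-level end of study removes it for early finishers but not for the last volunteers. The figure should not be read as days with no reporting duty at all, because the untimed sentence on outcomes may apply.

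The objectives, endpoints, analysis sets, sample size and error rates are untouched. The correction is worth making because it concerns volunteer and partner safety, and because sites cannot apply the text consistently as it stands.

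**What to change.** Reconcile Section 5.1 item 10 with Section 13.3 so that they state the male duties on contraception and on fathering a child consistently. Reconcile the sentences of Section 13.3 so that the period covered by pregnancy notification is stated once, consistently with the restrictions it refers to, and so that its relation to the opening sentence on outcomes is clear. Where the text relies on the end of the study, say whether this is the volunteer's own last visit or the trial-level end in Section 9.5. The sponsor's physician decides the durations; none is proposed here.

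The cost is a wording amendment, a check that the consent form matches, and possibly a few notifications after the last visit. Notification depends on the investigator receiving information, so no visit, test or sample is added.
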